3. SUBJECT SELECTION

A total of 3 pilot participants in Phase I and 62 participants in Phase II with elevated repetitive negative thinking (RNT) will participate in the proposed study. Participants will be selected based on the inclusion/exclusion criteria described below:

Inclusion criteria

- 1) Adults ages 18-60 years old
- 2) Right-handed, as assessed by the Edinburgh Handedness Inventory (score ≥ 61)
- 3) Living in Massachusetts
- 4) RNT in the form of mental rituals, worries, and/or depressive ruminations is the primary reason for seeking treatment (i.e., RNT is not better characterized by another disorder; e.g., post-traumatic stress disorder). Patients who present with multiple forms of RNT (e.g., mental rituals and worries), will be included to ensure generalizability and will be able to address each of these thinking patterns in treatment.
- 5) RNT severe enough to warrant intervention based on:
 - a. Moderate impairment on the Work and Social Adjustment Scale (WSAS total score ≥ 15 and ≥ 4 on any of the 5 sub-scales)
 - b. Score above the clinical mean on the Perseverative Thinking Questionnaire – Past Week (PTQ-PW ≥ 37)
- 6) Fluent in English, willing to provide informed consent, and willing to comply with the study protocol
- 7) Access to a device with an internet connection, camera, and microphone (e.g., computer, smart phone, tablet)
- 8) Comfortable and capable of using a computer and completing reaction-time tasks
- 9) Psychiatric comorbidities not listed in exclusion criteria below will be allowed

Exclusion criteria

1. History of head injury resulting in prolonged loss of consciousness and/or neurological sequelae; History of seizures; History of stroke; Signs of increased intracranial pressure; Prior neurosurgical procedure
2. Current or history of neurologic or psychiatric disease (e.g., dementia, brain damage, or other cognitive impairment), mental retardation, or borderline intellectual functioning that would interfere with ability to participate in the study

3. Impaired (or uncorrected) vision, medical illness, or medical treatment that would likely interfere with participation
4. Active suicidal or homicidal ideation, as assessed by the Structured Clinical Interview for DSM-5-Research Version (SCID-5-RV), Structured Interview Guide for the Hamilton Depression Rating Scale (SIGH-D), and/or score on the Beck Depression Inventory (BDI-II) suicide item (#9) ≥ 2 , or any features requiring a higher level of care

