5. STUDY PROCEDURES

Overview

This is a single-site study at the MGH Richard B. Simches Research Center (Boston, MA) and Athinoula A. Martinos Center for Biomedical Imaging (Charlestown, MA). Eligible participants will complete: (1) 3 electroencephalogram (EEG) sessions which record brain activity while participants sit at rest (i.e., resting state functional connectivity) and perform a computer task (2 hours), (2) 3 computer task sessions in which participants view a series of images (i.e., faces, scenes), and we measure where on the screen they are looking using an eye tracker and the sweatiness of their palms (60-90 min), (3) an 8-week therapy protocol (60 minutes each) – with random assignment to either Attention Regulation – Emotion Regulation Therapy (AR-ERT) or supportive psychotherapy (SPT), and (4) 4 clinical assessment visits including clinician interviews and self-report measures at baseline (week 0), mid-treatment (week 4), post-treatment visit (week 8), and 3-month follow-up (week 20). The EEG sessions will take place at the Martinos Center and the computer task sessions will take place at the MGH Center for OCD and Related Disorders in Simches. Clinical assessments will take place virtually using Healthcare Secure Zoom™, an encrypted and HIPAA-compliant video conferencing platform (or over the phone). Treatment visits will also take place virtually and will be conducted using Healthcare Secure Zoom™ (or over the phone). Twenty-four hours prior to EEG and computer task sessions, participants will be screened for COVID-19 symptoms by completing the MGB COVID-19 Prescreen Questions. Subjects will be given the option of combining the screening and baseline clinical assessment visits (if they are deemed eligible for the study after screening) and combining the mid-treatment and post-treatment clinical assessment visits to their treatment session visits (to reduce subject burden). Thus, study participation may only involve 16 total visits if such visits are combined. To avoid dropout, subjects will be paid \$20 each for the baseline, mid-treatment, post-treatment, and 3-month follow-up clinical assessments, \$20 each for the 3 EEG sessions, and \$20 each for the 3 computer task visits (\$200 total). Participants who cannot afford to travel to the treatment facility will be provided with transportation fare (e.g., parking passes) to attend in-person study visits (\$12.50 x 3 computer task visits at the Simches Building + \$7 x 3 EEG sessions at the Martinos Center = \$58.50).

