6. BIOSTATISTICAL ANALYSIS

Overview

Data acquisition and analytics approaches will be performed by [name] under the supervision of biostatistician [name]. To characterize our sample, data will be displayed graphically, and summary statistics (e.g., means and frequencies) will be calculated for all variables, including demographic and clinical descriptors. Descriptive statistics and exploratory graphing (e.g., scatter plots) will be used to assess normality, skew, and outliers on all measures. Continuous measures will be transformed if necessary, to satisfy assumptions of normality and homogeneity of variance.

Baseline differences between the treatment arms (AR-ERT vs. SPT) in demographic and other potential prognostic variables will be examined using chi-square analyses for discrete variables and ANOVA for continuous variables. While randomization tends to produce well-balanced treatment samples, if we find significant differences in potentially important baseline variables, we will include these variables as covariates in subsequent multivariate analyses. Candidate covariates for adjustment include baseline values of RNT (PTQ-PW score), symptom measures (Y-BOCS, SIGH-A, SIGH-D), and use of psychotropic medication (yes/no). Additional covariates that are unlikely to moderate treatment effect, but nonetheless will be examined for completeness, include: age, gender, education, race/ethnicity (majority vs. minority as we do not anticipate recruiting enough subjects from any one minority group to perform analyses for specific groups). If effects of gender and/or minority status are found that might be clinically meaningful, even if not statistically significant, we will report these to guide future research. Frequencies of adverse events (with 95% confidence intervals) will be calculated by treatment arm and type of event. We also will compare treatment groups on baseline credibility/expectancy of treatment and post-treatment satisfaction. A two-tailed p value $<.05$ will be considered evidence of statistical significance for the primary outcome.

Missing Data

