- 2) **Electrophysiological:** (a) proactive cognitive control in anticipation of conflict (i.e., cue-locked N2 ERP amplitudes on “opposite” vs. “actual” trials; CECT), and (b) reactive cognitive control in response to conflict (i.e., target-locked N2, N450, and P300 ERP amplitudes after the “opposite” vs. “actual” cue; CECT),
- 3) **Self-report:** Attentional Control Scale (ACS).

We will analyze each target index individually without adjusting for multiple testing¹²⁸ in order to be inclusive in identifying targets for future studies (e.g., R61/R33 proposal). Analyses will be modeled as the GLM equivalent of 2 x 3 ANOVAs with treatment condition (AR-ERT vs. SPT), time (pre-, mid-, post-treatment), and their interaction as fixed effects; the primary contrast of interest will be treatment difference at week 8 (post-treatment).¹²⁹ Repeated measures per person will be modeled with either an auto-correlation, Toeplitz, or unstructured covariance matrix (choosing the best model based on AIC and BIC).

Hypothesis 2a: Treatment Efficacy. To examine whether repetitive negative thinking (RNT) and psychiatric functioning improve during AR-ERT, we will also use GLM. Analyses will be modeled as the GLM equivalent of 2 x 4 ANOVAs with treatment condition (AR-ERT vs. SPT), time (pre-, mid-, post-treatment, follow-up), and their interaction as fixed effects; the primary contrast of interest will be treatment difference at week 8 (post-treatment), and a secondary outcome contrast will be at week 20 (3-month follow-up). Outcomes include:

- 1) **Repetitive Negative Thinking:** (a) Perseverative Thinking Questionnaire – Past Week (PTQ-PW; primary outcome), (b) Rumination Response Scale (RRS), (c) Penn State Worry Questionnaire (PSWQ), and (d) Rumination on Obsessions and Compulsions Scale (ROCS).

- 2) **Clinical Symptoms:** (a) Yale-Brown Obsessive Compulsive Scale (Y-BOCS) and Dimensional Obsessive-Compulsive Scale (DOCS), (b) Structured Interview Guide for the Hamilton Anxiety Rating Scale (SIGH-A) and State Trait Anxiety Inventory-Trait (STAI-T), (c) Structured Interview Guide for the Hamilton Depression Rating Scale (SIGH-D) and Beck Depression Inventory (BDI-II), and (d) Clinical Global Impression Scale – Severity (CGI-S).
- 3) **Psychiatric Functioning:** (a) Work and Social Adjustment Scale (WSAS), and (b) Quality of Life Enjoyment and Satisfaction Questionnaire – Short Form (Q-LES-Q-SF).

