In prior studies,^{31,140} ERT significantly improved mean levels of attentional control (ACS, our self-report target; 15.6%) and reduced RNT (PTQ-PW, our primary outcome; 37.2%) from pre- to post-treatment; with effect sizes of Hedge's $g = 1.65$ and 2.36 respectively in an open trial. ERT also significantly reduced worry (PSWQ; 34.8%) and rumination (RRS; 17.6%); with effect sizes of Hedge's $g = 1.50$ and 0.74 respectively compared to a waitlist control group with contact. Our electrophysiological and behavioral targets of attentional/cognitive control have also demonstrated sensitivity to intervention in previous studies.^{40,77,141} Sixty-two patients with elevated RNT (to balance power with recruitment feasibility) will enter the study to have a sample of 52 with attrition, which is reasonable given previous 85% retention rates of ERT at post-treatment (our primary endpoint).³¹ Based on power calculations (i.e., one-way ANOVA at post-treatment, assuming a 1:1 randomization to AR-ERT vs. SPT), with $n = 52$ completers, we will have 80% power to see a difference at .05 sig. level if the true effect size is 0.8 or greater

which is within range of the previous studies cited above. Finally, with 52 people at the end of treatment, we can detect correlations between target and outcome measures of .38 or greater.

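### Covariance structure is chosen by AIC and BIC with no tie-break; if BIC decides, the week-8 PTQ-PW test may run at about 6–9% error, depending on visit SDs the plan does not give

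*Combined protocol and SAP*

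**What the plan says.** The covariance sentence stands in Section 6, Primary Analyses, under Hypothesis 1. Repeated measures are modelled "with either an auto-correlation, Toeplitz, or unstructured covariance matrix (choosing the best model based on AIC and BIC"). The plan does not say whether AR and Toeplitz are the constant-variance or the heterogeneous-variance forms, which criterion decides, which definition of BIC applies, or which degrees-of-freedom method is used.

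Hypothesis 2a, which contains PTQ-PW, uses the same modelling approach with "time (pre-, mid-, post-treatment, follow-up), and their interaction as fixed effects" and has no covariance sentence of its own. Its contrasts are explicit: "the primary contrast of interest will be treatment difference at week 8 (post-treatment), and a secondary outcome contrast will be at week 20". The visits are "baseline (week 0), mid-treatment (week 4), post-treatment visit (week 8), and 3-month follow-up (week 20"). The Overview of Section 6 states that a two-tailed p below .05 "will be considered evidence of statistical significance for the primary outcome".

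Inclusion criterion 5b in Section 3 selects on the primary outcome itself: "Score above the clinical mean on the Perseverative Thinking Questionnaire", with a threshold of 37. No PTQ-PW standard deviation or between-visit correlation appears anywhere.

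**The concern.** The primary contrast is a difference between arms at one visit, so its standard error should reflect the variance at that visit. A constant-variance AR or Toeplitz structure estimates one variance from weeks 0, 4, 8 and 20 together. If the entry cut narrows the baseline spread, the pooled variance falls below the week-8 variance, the interval is too narrow, and the test rejects too often.

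For four visits, AR has 2 covariance parameters, Toeplitz 4 and unstructured 10. BIC penalises the extra parameters heavily at this sample size and tends to keep a constant-variance form. AIC penalises them less. Naming both without a tie-break leaves the primary test's error rate dependent on a decision that can be made after both fits have been seen.

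**Working it through.** **Inputs from the documents.** 62 randomised, 52 completers, "assuming a 1:1 randomization to AR-ERT vs. SPT" (so 26 per arm); two-sided .05; contrast at week 8; four visits; entry at PTQ-PW ≥ 37.

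**The plan's own figure.** The plan states that "we will have 80% power to see a difference at .05 sig. level if the true effect size is 0.8 or greater", from a one-way ANOVA at post-treatment. With 26 per arm the noncentrality is 0.8 × √(26/2) = 2.884, and the critical t on 50 df is 2.009. Power from the noncentral t is 80.7%, so the figure reproduces. It uses week 8 only and does not involve the covariance structure.

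**Assumed inputs.** SDs at weeks 0/4/8/20, relative to week 8, as listed below. Correlations: an irregular set (0–4 .5, 0–8 .4, 0–20 .3, 4–8 .7, 4–20 .55, 8–20 .65), AR(1) at .4 or .7, or Toeplitz .65/.5/.4.

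**Step 1: large-sample error if constant variance is always used.** With complete data and arm-by-visit means, the estimate is the difference in week-8 means. Its true SE is σ₈√(2/26), and the model uses about σ_pooled√(2/26). The error rate is 2 × [1 − Φ(1.96 × √R)], where R = mean variance over visits ÷ week-8 variance.

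- 0.8/0.9/1/1: R = (0.64 + 0.81 + 1 + 1)/4 = 0.8625, critical value 1.820, error 6.9%.
- 0.7/0.85/1/1: R = (0.49 + 0.7225 + 1 + 1)/4 = 0.803, critical value 1.757, error 7.9%.
- 0.6/0.8/1/1: R = (0.36 + 0.64 + 1 + 1)/4 = 0.75, critical value 1.697, error 9.0%.
- 1/1/0.8/0.8: R = 0.82/0.64 = 1.281, critical value 2.219, error 2.7%.

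**Step 2: is a ratio of 0.6–0.8 plausible?** If scores are normal and cut at their mean, the baseline SD falls to √(1 − 2/π) = 0.603 of its uncut value. With a baseline–week 8 correlation of .4, the week-8 SD becomes √(1 − 0.16 × 2/π) = 0.948. The ratio is 0.603/0.948 = 0.64, from the cut alone.

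**Step 3: error under the plan's selection rule.** REML fits of constant-variance AR(1), constant-variance Toeplitz and unstructured covariance to null trials with 26 per arm and complete data. There were 1,000 to 6,000 trials per setting (Monte Carlo SE about 0.3–0.9 points). Ranges cover the correlation sets and BIC on log subjects or log observations.

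| SD pattern | BIC decides | AIC decides | AIC and BIC disagree (irregular correlations) |
|---|---|---|---|
| 0.8/0.9/1/1 | 6.4–7.2% | 5.9–6.6% | 46–49% |
| 0.7/0.85/1/1 | 7.4–7.7% | 5.8–6.1% | 61–66% |
| 0.6/0.8/1/1 | 6.8–9.2% | 4.6–6.0% | 62–86% |
| Entry cut alone | 6.4–7.7% | 5.2–5.7% | 62–83% |
| 1/1/0.8/0.8 | 2.2–2.5% | 3.4–3.5% | – |

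Unstructured covariance gave 4.4–5.8% throughout. For 0.7/0.85/1/1 one 1,000-trial run gave 9.0% under BIC. Larger runs did not reproduce it and Step 1 gives 7.9%, so it is left out. The upper ends of the first row come from that same smaller run. Across the AR(1) and Toeplitz correlation sets the disagreement rate was lower, about 15–64%.

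**Step 4: which structure is chosen.** For 0.6/0.8/1/1 with the AR(1) and Toeplitz correlations, AIC picked unstructured in 86–95% of trials, BIC on log subjects in 21–38%, and BIC on log observations in 3–8%.

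**Step 5: dropout and baseline handling.** With 62 randomised and about 15% missing at week 8, 0.6/0.8/1/1 gave 7.5–8.0% (BIC), 4.9% (AIC) and 4.4% (unstructured). Constraining the arms to a common baseline mean gave 7.4%, 5.6% and 5.5%.

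**The case against.** A reader might infer that the plan's rule makes the primary test run near 9%. The documents do not support that.

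- **The SDs are assumed.** Values near 9% need strong heterogeneity, constant-variance forms and BIC as the deciding criterion. Heterogeneous AR or Toeplitz is not excluded by the text.
- **The two criteria do not both favour constant variance.** Unstructured is among the candidates, and where heterogeneity is strong AIC usually selects it and brings the error back to about 5–6%. The tendency belongs to BIC.
- **The direction is not fixed.** A lower week-8 variance makes the test conservative.
- **The entry cut acts on the screening score.** PTQ-PW is repeated at baseline when more than 7 days have passed since screening (Table 1 footnote). With an assumed retest correlation of .8–.9, the baseline/week-8 SD ratio is then about .72–.84, at the milder end or just beyond it. Nothing in the documents shows that scores spread out further during therapy.
- **The sentence sits under Hypothesis 1.** Those visits (weeks 0, 4, 8) are equally spaced and none of the target measures gates entry. Applying the rule to PTQ-PW is an inference. Unequal spacing in Hypothesis 2a also matters little for this contrast: with complete data and arm-by-visit means, it is the week-8 variance that counts.

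All of this limits the size. It does not rescue the rule. PTQ-PW either inherits a selection rule with no tie-break or has no covariance rule at all. The Overview's provision for transforming measures does not name variance across visits and would not undo selection on the outcome.

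**Conclusion.** The point holds as a conditional one. If AR and Toeplitz mean their constant-variance forms and baseline SD is 0.6–0.8 of week-8 SD, error for the primary week-8 contrast is about 6–9% when BIC decides and about 5–6% when AIC decides, against about 5% with unstructured covariance. If week-8 variance is lower than at other visits, error is about 2–4% and power is lost instead. The actual figure cannot be derived from the documents.

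What needs no assumption about SDs is that two criteria are named, they can choose different structures, and nothing says which prevails. This is a worthwhile improvement to error control in a pilot trial, to be made before outcome data are analysed. It is not a flaw that invalidates the design.

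**What to change.** Replace the selection clause with one sentence covering all Hypothesis 1 and Hypothesis 2a models: unstructured covariance, with Kenward-Roger or Satterthwaite degrees of freedom (name one). Only if that model fails to converge, move to heterogeneous-variance Toeplitz and then to heterogeneous-variance AR, in that order. Delete the AIC/BIC selection and state explicitly that the sentence applies to PTQ-PW.

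The cost is 6 covariance parameters for three visits or 10 for four, and slightly fewer degrees of freedom if the variances are in fact equal. With complete data and arm-by-visit means the point estimate does not change. The stated 80% power is unaffected, because it was computed at week 8 only.

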Our multi-level generalized linear modeling (GLM) approach (described below under “Primary Analyses”) uses an intent-to-treat analysis that includes all participants, regardless of missing data (increasing power and generalizability), and it provides accurate estimates of regression coefficients in small samples.^{118,119} Despite our best efforts to retain participants, we do expect dropouts (i.e., subjects who are lost to follow-up or withdraw early from the study for reasons described below under “Participant Withdrawal”). We will attempt to perform all scheduled assessments for subjects who are withdrawn from the protocol and will provide financial incentives for participation in assessments.

Missing data rates and patterns will be assessed by treatment arm. Reason(s) for missing data will be documented, and we will evaluate reasons for dropout, study withdrawal, and loss-to-follow-up by treatment group. We will attempt to ascertain if missingness is occurring at random by evaluating factors associated with dropout for potential attrition bias. We will also compare study dropouts to study completers on demographic and clinical variables. Finally, we will use sensitivity analyses to quantify the impact of missing data.¹²⁰

Data Processing

For behavioral tasks that include reaction times (e.g., the Emotional Interference Task [EIT]), we will remove reaction times <150 ms given that such responses are rare and likely represent errors.¹²¹ Eye position fixations from the Attentional Engagement-Disengagement Task (AEDT) sampled at 120Hz will be converted to visual fixation data using standard criteria (i.e., minimum duration 100ms; minimum radius 1 degree).¹²²

Eye-blink artifacts will be removed from scalp-recorded EEG data on the Cued

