Hypothesis 2b: Target Validation. To examine the extent to which alteration in the hypothesized target (attentional/cognitive control) is related to improvements in clinical RNT outcomes, we will compute change scores from pre- to post-treatment for both the target (i.e., AEDT, EIT, CECT, ACS) and outcome measures (i.e., PTQ-PW [primary outcome], RRS, PSWQ, ROCS, Y-BOCS, DOCS, SIGH-A, STAI-T, SIGH-D, BDI-II, CGI-S, WSAS, Q-LES-Q-SF). Pearson's correlations between changes in target and changes in outcome measures will then be computed (i.e., a completers-only analysis).

Exploratory Source Localization Analyses

We will also conduct exploratory source localization analyses with a focus on the frontoparietal (FPN) and default mode (DMN) networks. Based on previous research demonstrating changes in the anterior cingulate cortex (ACC) over the course of psychosocial treatment^{130,131} and indicating that increased activity in this region predicts better treatment outcomes,^{79,132–134} we will test the following:

1. Whether changes in ACC activation are demonstrated pre/post treatment using GLM (i.e., predicting a main effect of time) and whether treatment group (AR-ERT vs. SPT) moderates this effect (i.e., treatment group x time interaction).
2. Whether baseline (week 0) rostral ACC (rACC) theta (4.5-7 Hz) current density predicts greater reduction in RNT and symptom severity as measured by the PTQ-PW and disorder-specific measures using GLM (i.e., predicting a rACC theta x time interaction) and whether treatment group (AR-ERT vs. SPT) moderates this effect (i.e., treatment group x rACC theta x time interaction).

Finally, source localization analyses will be used to investigate the neural generators of scalp-recorded EEG signals during the CECT, with a focus on the dorsal anterior cingulate cortex (dACC) and dorsolateral prefrontal cortex (DLPFC) given their roles in conflict monitoring (dACC) and conflict resolution (DLPFC), respectively.^{57,58,135–139}

Power Analysis and Sample Size

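### Target validation (Hypothesis 2b) correlates change scores with no term for treatment arm, so a treatment effect on both measures can produce a correlation without any within-arm link

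*Combined protocol and SAP*

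**What the plan says.** All references are to the combined protocol and SAP.

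- **Section 6, Hypothesis 2b.** Pre-to-post change scores are formed "for both the target (i.e., AEDT, EIT, CECT, ACS) and outcome measures". The outcome list is "PTQ-PW [primary outcome], RRS, PSWQ, ROCS, Y-BOCS, DOCS, SIGH-A, STAI-T, SIGH-D, BDI-II, CGI-S, WSAS, Q-LES-Q-SF". Pearson's coefficient is then applied: "correlations between changes in target and changes in outcome measures will then be computed (i.e., a completers-only analysis". No arm term, stratification or within-arm estimate is mentioned.
- **Section 6, Power Analysis and Sample Size.** "with 52 people at the end of treatment, we can detect correlations between target and outcome measures of .38 or greater". The 52 are all expected completers of the 62 randomised 1:1, so about 26 per arm. Pooling is therefore inferred from the sample size; the plan does not state it in words.
- **Section 2, Specific Aims.** Hypothesis 1 predicts that AR-ERT beats SPT on the target. Hypothesis 2a predicts the same for the clinical outcomes.
- **Section 6, Missing Data and Primary Analyses.** The multilevel model is introduced as the approach to every hypothesis, and it "uses an intent-to-treat analysis that includes all participants, regardless of missing data". Hypothesis 2b does not use it.
- **Section 6, Hypothesis 1.** The decision not to adjust for multiple testing is written for the target indices in that hypothesis. Hypothesis 2b has no multiplicity rule of its own.

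**The concern.** Hypothesis 2b is the only planned test that links change in the target to change in outcome. It should show whether patients whose attentional or cognitive control improved more also had more clinical improvement.

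A pooled correlation mixes two things: the association between patients within an arm, and the separation of the two arm means. If AR-ERT shifts both measures relative to SPT, the two clouds of points lie apart along both axes. The pooled coefficient then leaves zero even if, within each arm, target change says nothing about outcome change. The planned statistic cannot distinguish a target related to outcome from two parallel treatment effects. The distortion grows as Hypotheses 1 and 2a do better, which is when Hypothesis 2b is most likely to be cited.

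**Working it through.** **1. The plan's own figure.** By Fisher's z, with 52 pairs, 80% power and two-sided .05 (both levels are stated for the group comparison; the correlation sentence gives neither):

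r_min = tanh[(1.960 + 0.842)/√(52 − 3)] = tanh(0.400) = 0.380.

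The stated .38 is correct and matches the use of all 52 completers.

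**2. Correlation induced by arm alone.** Let the within-arm SD of each change score be 1, the within-arm correlation 0, allocation 1:1, and the between-arm differences dx (target) and dy (outcome), both scored so that positive means improvement. The arm indicator has variance 1/4, so the pooled covariance is dx·dy/4 and the pooled variances are 1 + dx²/4 and 1 + dy²/4:

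r = (dx·dy/4) / √[(1 + dx²/4)(1 + dy²/4)].

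- 0.5 and 0.5: 0.0625/1.0625 = 0.059
- 0.8 and 0.8: 0.16/1.16 = 0.138
- 1.0 and 1.0: 0.25/1.25 = 0.200
- 0.8 and 0: 0

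The values of dx and dy are assumptions. The documents give neither an effect against SPT nor a change-score SD for any target index or outcome. The value 0.8 is borrowed from the group comparison, where "we will have 80% power to see a difference at .05 sig. level if the true effect size is 0.8 or greater"; that effect refers to post-treatment scores.

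**3. Rejection rates.** With 52 pairs the two-sided 5% threshold is |r| = 0.273. Simulation with 100,000 replicates per row, normal data, 26 per arm and zero within-arm correlation:

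| dx / dy (SD of change) | Induced r | Rejects, raw correlation | Rejects, arm-adjusted |
|---|---|---|---|
| 0 / 0 | 0 | 5.0% | 5.0% |
| 0.8 / 0 | 0 | 4.9% | 4.9% |
| 0.5 / 0.5 | 0.06 | 6.9% | 4.9% |
| 0.5 / 0.8 | 0.09 | 9.8% | 4.9% |
| 0.8 / 0.8 | 0.14 | 16.6% | 5.0% |
| 1.0 / 1.0 | 0.20 | 30.3% | 4.9% |

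To induce the threshold of 0.273 by arm effects alone, two equal effects of 2√(0.273/0.727) = 1.23 SD are needed. To induce .38 they must be 2√(0.38/0.62) = 1.57 SD.

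**4. Price of adjusting for arm.** One covariate: r_min = tanh(2.802/√(52 − 4)) = 0.384. A single arm of 26: r_min = tanh(2.802/√(26 − 3)) = 0.53.

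**5. Number of pairs.** Hypothesis 2b names four target measures and 13 outcomes: 4 × 13 = 52 pairs. Hypothesis 1 splits the CECT into one proactive index ("cue-locked N2 ERP amplitudes on" high- against low-conflict trials) and three reactive ones ("target-locked N2, N450, and P300 ERP amplitudes after the" cue). That makes seven indices and 7 × 13 = 91 pairs. If no true associations exist and each test holds its 5% level, the expected number of false positives is 52 × .05 = 2.6 or 91 × .05 = 4.6. For PTQ-PW alone with seven indices it is 7 × .05 = 0.35. The documents do not say which count applies.

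**The case against.** The best defence is one of scope. Target validation belongs to the Secondary Aim, section 1 calls it preliminary, and the trial is a pilot. The hypothesis speaks of association and makes no mediation claim. The completers-only restriction is declared openly, the Missing Data section promises sensitivity analyses, and withdrawn patients are asked to complete the remaining assessments. All of this stands, and it lowers the severity. It does not remove the bias: an association produced by the difference between arms is not the patient-level association that the hypothesis describes.

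The size is also modest. At 0.8 SD on both measures the test still fails to reject about 83% of the time when there is no within-arm link.

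Three stronger readings are tempting, and the documents support none of them:

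- A reader might infer that success on Hypotheses 1 and 2a guarantees success on 2b. The rates above contradict that.
- A reader might put the cited effects of 1.65 (ACS) and 2.36 (PTQ-PW) into the formula. The power section describes these as pre-to-post effects from an open trial. They are not differences from SPT and are not shown to be on the change-score SD scale.
- A reader might say that nothing in Hypothesis 2b is prioritised. PTQ-PW is marked there as the primary outcome; what is missing is any order among the target indices and the other 12 outcomes.

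**Conclusion.** The point holds at moderate severity. As written, Hypothesis 2b can reject more often than 5% when target change and outcome change are unrelated within both arms, provided AR-ERT moves both measures. The rate is about 7% at 0.5 SD on both, 17% at 0.8 and 30% at 1.0, and there is no inflation if only one measure responds.

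This rests on three assumptions: that the arms are pooled, as n = 52 implies; that the between-arm effects are on the change-score SD scale; and that the data are roughly normal with 26 completers per arm. The plan's detectable correlation of .38 is right, and Hypotheses 1 and 2a are unaffected. The departure from the all-participants approach and the lack of a multiplicity rule are secondary matters.

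**What to change.** **Main change.** Under Hypothesis 2b, replace the raw correlation with a regression of outcome change on target change that includes treatment arm, reported as a partial correlation given arm. Show the within-arm estimates descriptively only, since 26 patients would need a correlation of about .53 for 80% power. The cost is SAP wording, one degree of freedom, a detectable correlation of .384 instead of .380, and somewhat smaller reported correlations. No new data are needed.

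**Optional and secondary.**

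- Adjust for the baseline values of both measures, at the cost of further degrees of freedom.
- Add a sensitivity analysis that keeps participants with missing data, or state that Hypothesis 2b is an exception to the general modelling approach.
- Name PTQ-PW with the target indices as the key set, label the remaining pairs descriptive, and say whether the CECT counts as one index or four.

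Formal error control over the key set is a separate choice with a real price. Bonferroni over seven tests raises the detectable correlation to about .47 and cuts power at .38 to about 54%. In a pilot, labelling the other pairs descriptive may be enough.
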